## 14.6. Event Intensity (severity):

**Mild:** Transient, needing no special treatment, and/or does not interfere with the subject's daily activity.

**Moderate:** Low level of inconvenience or concern to the subject and may interfere with daily activities, but is usually improved by simple therapeutic remedy.

**Severe\*:** Interrupts a subject's daily activity and typically requires intervening treatment.

**Please Note\*:** The terms “serious” and “severe” are not synonymous. Severe is often used to describe the intensity (severity) of a specific event (as in mild, moderate, or severe myocardial infarction); the event itself, however, may be of relatively minor medical significance (such as severe headache). This is NOT the same as “serious” which is based on the definition of “serious criteria” which have been provided.

## 15. Administrative Considerations

### 15.1. Document Storage and Retention

The Sponsor and Investigator will retain all records and documents pertaining to this study. They will be available for inspection by the appropriate regulatory agencies. In addition, the Investigator will retain the

source documents from which the information entered on the eCRF was derived. These records are to be retained in a secure storage facility maintained by the Investigational Center until 2 years after approval of the above-listed study devices or termination of the study, whichever is longer. The Investigator should not dispose of these records without the approval of the Sponsor.

## 15.2. Data Handling

All data required for analysis will be captured on electronic Case Report Forms (eCRFs) using Oracle Clinical's 21 CFR Part 11 compliant Remote Data Capture (RDC) module. Original eCRFs will not be used as source data and supporting documentation will be required. Electronic device data will be collected from the Medtronic MiniMed® 530G pump using Medtronic CareLink Clinical, which is 21 CFR Part 11 compliant.

The Investigator will ensure that all eCRFs are completed promptly, completely, and accurately. Information on case report forms must conform to the information in the source documents. Medtronic will provide detailed instructions to assist with CRF completion. In the event of data discrepancies, Investigational Centers will be asked to resolve queries electronically in the RDC system; otherwise, irresolvable data-related issues will be routed to the Sponsor for review and final disposition. An audit trail is maintained in Oracle Clinical to capture any corrections or changes of the eCRFs. System backups for data stored in the Oracle Clinical system will be consistent with Medtronic standard procedures.

Medtronic will only consider eCRFs to be complete when all discrepancies between source data and eCRF have been resolved and eCRF content has been reviewed by a Study Monitor. In addition, specific eCRFs must also be reviewed and electronically signed by the Investigator, indicating his/her agreement with the accuracy of all recorded data. It is expected that the Investigator and his/her staff will cooperate with the monitoring team and provide any missing data in a timely manner.

## 15.3. Data Preparation

Prior to data extraction, all collected data will undergo a final verification by Data Management. Documentation of this verification will be maintained in the sponsor study files. Upon the completion of the verification, data will be extracted and transferred to the appropriate personnel for analysis.

## 15.4. Training of Clinical Staff

Training of the Investigational Center staff on study procedures will be initiated before the protocol is implemented.

## 15.5. Study Binders

A Regulatory Binder and an Investigator/Coordinator Manual will be provided by the Sponsor to be maintained by Investigational Center staff. At a minimum, each Regulatory Binder will include:

- Study Contact Sheet
- Clinical Study Agreement(s)
- Signed/dated CV of Investigator(s)
- IRB Correspondence
- IRB-approved Protocol(s) and Informed Consent Form(s), including all amendments
- Clinical Bulletins- A brief official update or summary of current study news on a matter of immediate interest and high importance to Investigational Center surrounding the study protocol.
- Site Visit Sign-In Log

- Study Correspondence
- Site Signature and Study Delegation Log
- Training Records
- Sound Bites

At a minimum, the Investigator/Coordinator Manual will include:

- Sample Coordinator Worksheets
- User Guide(s), Instructions for Use, and/or User Manual as applicable
- Quick Reference Guide
- Training materials

## **15.6. Publication Policy**

The contents of this protocol, the manuals pertaining to this study and the results of the investigation are confidential and may not be published or disclosed without the written consent of Medtronic Diabetes. The identity of the subjects may not be disclosed, unless required by law, to any persons not immediately involved in the study or the study procedures.

## 18. Appendices

## 18.1. Validated Study Questionnaires

### 18.1.1. Hypoglycemia Unawareness Questionnaire

1. Check the category that best describes you: (check one only)  
\_\_\_\_\_ I always have symptoms when my blood sugar is low (A)  
\_\_\_\_\_ I sometimes have symptoms when my blood sugar is low (R)  
\_\_\_\_\_ I no longer have symptoms when my blood sugar is low (R)
2. Have you lost some of the symptoms that used to occur when your blood sugar was low?  
\_\_\_\_\_ yes (R) \_\_\_\_\_ no (A)
3. In the past six months how often have you had moderate hypoglycemia episodes?  
(Episodes where you might feel confused, disoriented, or lethargic and were unable to treat yourself)  
\_\_\_\_\_ Never (A) \_\_\_\_\_ Once or twice (R) \_\_\_\_\_ Every other month (R)  
\_\_\_\_\_ Once a month (R) \_\_\_\_\_ More than once a month (R)
4. In the past year how often have you had severe hypoglycemic episodes? (Episodes where you were unconscious or had a seizure and needed glucagon or intravenous glucose)  
\_\_\_\_\_ Never (A) \_\_\_\_\_ 1 time (R) \_\_\_\_\_ 2 times (R) \_\_\_\_\_ 3 times (R)  
\_\_\_\_\_ 5 times (R) \_\_\_\_\_ 6 times (R) \_\_\_\_\_ 7 times (R) \_\_\_\_\_ 8 times (R)  
\_\_\_\_\_ 9 times (R) \_\_\_\_\_ 10 times (R) \_\_\_\_\_ 11 times (R)  
\_\_\_\_\_ 12 or more times (U)
5. How often in the last month have you had readings <70 mg/dl with symptoms?  
\_\_\_ Never \_\_\_ 1 to 3 times \_\_\_ 1 time/week \_\_\_ 2 to 3 times/week \_\_\_ 4 to 5 times/week  
\_\_\_ Almost daily
6. How often in the last month have you had readings <70 mg/dl without any symptoms?  
\_\_\_\_\_ Never \_\_\_\_\_ 1 to 3 times \_\_\_\_\_ 1 time/week \_\_\_\_\_ 2 to 3 times/week  
\_\_\_\_\_ 4 to 5 times/week \_\_\_\_\_ Almost daily  
(R = answer to 5 > answer to 6, A = answer to 6 > answer to 5)
7. How low does your blood sugar need to go before you feel symptoms?  
\_\_\_\_\_ 60-69 mg/dl (A) \_\_\_\_\_ 50-59 mg/dl (A) \_\_\_\_\_ 40-49 mg/dl (R)  
\_\_\_\_\_ <40 mg/dl (R)
8. To what extent can you tell by your symptoms that your blood sugar is low?  
\_\_\_\_\_ Never (R) \_\_\_\_\_ Rarely (R) \_\_\_\_\_ Sometimes (R) \_\_\_\_\_ Often (A)  
\_\_\_\_\_ Always (A)

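### The printed scoring key for questions 5 and 6 of the Hypoglycemia Unawareness Questionnaire runs opposite to the form's other symptom items and can misplace subjects near the awareness cut-off

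*Protocol*

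**What the plan says.** The form in Protocol 18.1.1 has eight questions, each scored A or R, with questions 5 and 6 scored jointly, so there are seven scored items. Question 5 asks "How often in the last month have you had readings <70 mg/dl with symptoms" and question 6 asks "How often in the last month have you had readings <70 mg/dl without any symptoms". Both offer the same six frequency options, listed from never up to almost daily. The key printed under question 6 is "R = answer to 5 > answer to 6, A = answer to 6 > answer to 5".

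The form is completed at Visit 1 and again at Visit 5 (Protocol Table 1, 11.3.1 and 11.7.1). Its result is used in three places:

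- as intact versus impaired strata, each with a 95% confidence interval, in the descriptive A1C summaries (Protocol 7.1.3.3; SAP 7.2.1.2; also the Synopsis list of A1C subgroups);
- as the same strata in the adverse-event summaries (Protocol 7.1.4; SAP 7.2.2; also the Synopsis safety endpoints);
- as a change in score from baseline to end of study (Protocol 7.1.6; SAP 7.2.4.9).

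The readable text gives no rule for equal answers to 5 and 6 and no cut-off between intact and impaired. Pages 20 to 52 of the SAP could not be read in the copy reviewed, so neither rule is claimed to be missing from the plan.

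**The concern.** Taken literally, the key gives R to subjects whose lows come mostly with symptoms and A to those whose lows come mostly without them. On the rest of the form, R goes with lost or absent symptoms. The 5/6 item therefore counts against the construct that the other symptom items measure.

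The device suspends insulin at low glucose, so awareness of lows is a natural stratum for reading severe hypoglycemia events. If the printed key was programmed, some aware subjects would be reported as impaired and some unaware subjects as intact. Errors in both directions can blur the contrast that the strata are meant to show.

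**Working it through.** No figure in the plan can be reproduced here, so the check is one of direction followed by simple counting.

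**Step 1. Direction of each symptom item on the form**

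| Item | Retained symptoms | Lost or absent symptoms |
|---|---|---|
| 1, general statement | always has symptoms: A | no longer has symptoms: R |
| 2, "Have you lost some of the symptoms that used to occur when your blood sugar was low" | no: A | yes: R |
| 7, "How low does your blood sugar need to go before you feel symptoms" | 60-69 or 50-59 mg/dl: A | 40-49 or <40 mg/dl: R |
| 8, "To what extent can you tell by your symptoms that your blood sugar is low" | often or always: A | never, rarely or sometimes: R |
| 5/6, as printed | 5 > 6: **R** | 6 > 5: **A** |

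Four items agree with each other, and the 5/6 item contradicts all four.

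**Step 2. The extreme answers**

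- Question 5 almost daily, question 6 never (every low is felt): the printed key gives R; the direction of items 1, 2, 7 and 8 gives A.
- Question 5 never, question 6 almost daily (no low is felt): the printed key gives A; the direction of the other items gives R.

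**Step 3. Effect on the stratum**

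Assume that a subject is impaired if the number of R answers is at least k. Let T be the R count on the other six items (1, 2, 3, 4, 7, 8), so T runs from 0 to 6.

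| Answers | R count, printed key | R count, consistent key |
|---|---|---|
| 5 > 6 | T + 1 | T |
| 6 > 5 | T | T + 1 |
| equal | same under both keys | same under both keys |

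The two counts fall on opposite sides of k only when T < k and T + 1 ≥ k, that is, when T = k − 1. For each k from 1 to 7, that is exactly one of the seven possible values of T. At that value:

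- 5 > 6 gives T + 1 = k under the printed key (impaired) and T = k − 1 under the consistent key (intact);
- 6 > 5 gives the reverse.

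**Step 4. Effect on the change score**

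This is the R contribution of the 5/6 item at Visit 5 minus that at Visit 1, with a tie scored t under both keys.

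| Ordering, Visit 1 to Visit 5 | Printed | Consistent | Size of error |
|---|---|---|---|
| 5 > 6 at both | 1 − 1 = 0 | 0 − 0 = 0 | 0 |
| 6 > 5 at both | 0 − 0 = 0 | 1 − 1 = 0 | 0 |
| 5 > 6 to tie | t − 1 | t − 0 | 1 |
| 6 > 5 to tie | t − 0 | t − 1 | 1 |
| 5 > 6 to 6 > 5 | 0 − 1 = −1 | 1 − 0 = +1 | 2, sign reversed |
| 6 > 5 to 5 > 6 | 1 − 0 = +1 | 0 − 1 = −1 | 2, sign reversed |

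Moves from a tie mirror moves to a tie and also give an error of 1. A subject whose ordering is stable has the wrong item score at each visit but the right change.

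**Step 5. Reach**

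The primary mixed model (Protocol 7.1.3.1; SAP 7.2.1) contains visit effects and random site and subject effects, and no questionnaire term. Adverse events receive no formal statistical analysis (Protocol 7.1.4; SAP 7.2.2). The effect is confined to descriptive outputs.

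**The case against.** The source instrument is not available here. The appendix presents its forms as validated, so the line could be a faithful copy and not a slip by the sponsor. Neither A nor R is defined, and reading > as more frequent relies on the order in which the options are listed. The consequence also needs several conditions together: the printed key was programmed, strata come from an R count, the answers to 5 and 6 differ, and the subject stands one R below the cut-off. Question 4 adds a further undefined code, U, for its top category. Finally, the one-in-seven statement is true of any binary item in a count score, so it does not measure impact in this trial.

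Much of this stands as a limit on size. The documents do not show which key was used, how U is counted, or how many subjects gave which answers. None of it removes the contradiction, because that does not depend on what the letters are called: four items point one way and 5/6 points the other. Only reverse coding of the frequency options, of which the readable text has no trace, would rescue the key. A text-extraction fault is unlikely, because both halves of the key agree with each other.

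**Conclusion.** The point holds as a minor one. Confidence is high that the printed 5/6 key runs against items 1, 2, 7 and 8.

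The consequence is conditional. If the printed key is applied and R answers are counted, one of the seven scored items is reversed. The count is then off by one whenever the answers to 5 and 6 differ. The stratum is wrong for subjects with unequal answers whose other six items total the cut-off minus one. The change score is wrong by 1 or 2 when the 5/6 ordering changes between visits.

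This rests on four assumptions: > means more frequent; strata are formed by an R-count cut-off; ties are scored alike under both keys; and U in question 4 enters the count in the same way under both keys. The number of misplaced subjects cannot be given. The primary non-inferiority conclusion on A1C is unaffected.

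**What to change.** Check the key for questions 5 and 6 against the source instrument and reverse the line in Protocol 18.1.1: R when the answer to 6 exceeds the answer to 5, and A when the answer to 5 exceeds the answer to 6. Should the source carry the key as printed, the report should say so and explain the conflict with the other items.

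Derive the awareness strata and the change score from the raw answers under the corrected key, and state in the report which key was programmed. At the same time, confirm that the rule for equal answers and the intact/impaired cut-off are written down beside the key.

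The cost is one document check, one corrected line and a re-run on answers already collected. There is no burden on sites or patients. If the programs already use the consistent direction, a sentence confirming this is enough alongside the corrected form.

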## 18.1.2. EQ-5D Questionnaire

### Adult Health Questionnaire

*(English version for the US)*

By placing a checkmark in one box in each group below, please indicate which statements best describe your own health state today.

#### Mobility

- I have no problems in walking about
- I have some problems in walking about
- I am confined to bed

#### Self-Care

- I have no problems with self-care
- I have some problems washing or dressing myself
- I am unable to wash or dress myself

#### Usual Activities *(e.g. work, study, housework, family or leisure activities)*

- I have no problems with performing my usual activities
- I have some problems with performing my usual activities
- I am unable to perform my usual activities

**Pain/Discomfort**

- I have no pain or discomfort
- I have moderate pain or discomfort
- I have extreme pain or discomfort

**Anxiety/Depression**

- I am not anxious or depressed
- I am moderately anxious or depressed
- I am extremely anxious or depressed

To help people say how good or bad a health state is, we have drawn a scale (rather like a thermometer) on which the best state you can imagine is marked 100 and the worst state you can imagine is marked 0.

We would like you to indicate on this scale how good or bad your own health is today, in your opinion. Please do this by drawing a line from the box below to whichever point on the scale indicates how good or bad your health state is today.

**Your own  
health state  
today**

Best  
imaginable  
health state

100

90

80

70

60

50

40

30

20

10

0

Worst  
imaginable  
health state

### 18.1.3. HFS Questionnaire

Study ID:

Subject ID:

#### Adult Low Blood Sugar Survey (University of Virginia)

I. **Behavior:** Below is a list of things people with diabetes sometimes do in order to avoid low blood sugar and its consequences. Circle one of the numbers to the right that best describes what you have done during the last 6 months in your daily routine to AVOID low blood sugar and its consequences. (Please do not skip any!).

	Never	Rarely	Some- times	Often	Almost Always
To avoid low blood sugar and how it affects me, I ...					
1. Ate large snacks.	0	1	2	3	4
2. Tried to keep my blood sugar above 150.	0	1	2	3	4
3. Reduced my insulin when my blood sugar was low.	0	1	2	3	4
4. Measured my blood sugar six or more times a day.	0	1	2	3	4
5. Made sure I had someone with me when I go out.	0	1	2	3	4
6. Limited my out of town travel.	0	1	2	3	4
7. Limited my driving (car, truck or bicycle).	0	1	2	3	4
8. Avoided visiting friends.	0	1	2	3	4
9. Stayed at home more than I liked.	0	1	2	3	4
10. Limited my exercise/physical activity.	0	1	2	3	4
11. Made sure there were other people around.	0	1	2	3	4
12. Avoided sex.	0	1	2	3	4
13. Kept my blood sugar higher than usual in social situations.	0	1	2	3	4
14. Kept my blood sugar higher than usual when doing important tasks.	0	1	2	3	4
15. Had people check on me several times during the day or night.	0	1	2	3	4

Study ID:

Subject ID:

II. Worry: Below is a list of concerns people with diabetes sometimes have about low blood sugar. Please read each item carefully (do not skip any). Circle one of the numbers to the right that best describes how often in the last 6 months you WORRIED about each item because of low blood sugar.

	Never	Rarely	Some- times	Often	Almost Always
Because my blood sugar could go low, I worried about...					
16. Not recognizing/realizing I was having low blood sugar.	0	1	2	3	4
17. Not having food,fruit, or juice available.	0	1	2	3	4
18. Passing out in public.	0	1	2	3	4
19. Embarrassing myself or my friends in a social situation.	0	1	2	3	4
20. Having a hypoglycemic episode while alone.	0	1	2	3	4
21. Appearing stupid or drunk.	0	1	2	3	4
22. Losing control.	0	1	2	3	4
23. No one being around to help me during a hypoglycemic episode.	0	1	2	3	4
24. Having a hypoglycemic episode while driving.	0	1	2	3	4
25. Making a mistake or having an accident.	0	1	2	3	4
26. Getting a bad evaluation or being criticized.	0	1	2	3	4
27. Difficulty thinking clearly when responsible for others.	0	1	2	3	4
28. Feeling lightheaded or dizzy.	0	1	2	3	4
29. Accidentally injuring myself or others.	0	1	2	3	4
30. Permanent injury or damage to my health or body.	0	1	2	3	4
31. Low blood sugar interfering with important things I was doing.	0	1	2	3	4
32. Becoming hypoglycemic during sleep.	0	1	2	3	4
33. Getting emotionally upset and difficult to deal with.	0	1	2	3	4

II. Worry: Below is a list of concerns people with diabetes sometimes have about low blood sugar. Please read each item carefully (do not skip any). Circle one of the numbers to the right that best describes how often in the last 6 months you WORRIED about each item because of low blood sugar.

	Never	Rarely	Some- times	Often	Almost Always
Because my blood sugar could go low, I worried about...					
16. Not recognizing/realizing I was having low blood sugar.	0	1	2	3	4
17. Not having food,fruit, or juice available.	0	1	2	3	4
18. Passing out in public.	0	1	2	3	4
19. Embarrassing myself or my friends in a social situation.	0	1	2	3	4
20. Having a hypoglycemic episode while alone.	0	1	2	3	4
21. Appearing stupid or drunk.	0	1	2	3	4
22. Losing control.	0	1	2	3	4
23. No one being around to help me during a hypoglycemic episode.	0	1	2	3	4
24. Having a hypoglycemic episode while driving.	0	1	2	3	4
25. Making a mistake or having an accident.	0	1	2	3	4
26. Getting a bad evaluation or being criticized.	0	1	2	3	4
27. Difficulty thinking clearly when responsible for others.	0	1	2	3	4
28. Feeling lightheaded or dizzy.	0	1	2	3	4
29. Accidentally injuring myself or others.	0	1	2	3	4
30. Permanent injury or damage to my health or body.	0	1	2	3	4
31. Low blood sugar interfering with important things I was doing.	0	1	2	3	4
32. Becoming hypoglycemic during sleep.	0	1	2	3	4
33. Getting emotionally upset and difficult to deal with.	0	1	2	3	4

## 18.1.4. EQ-5D Youth Proxy Questionnaire

Study ID:

Subject ID:

### Health Questionnaire

### Proxy Version for EQ-5D-Y

The purpose of this questionnaire is to explore how a care-giver or someone who knows the child well (proxy), thinks that the child would rate his/her own health. The proxy should answer as he/she thinks that the child would respond if he/she were able to fill in the questionnaire for him/herself.

## EQ-5D-Y

## Describing the child's health today

PLEASE ANSWER ON BEHALF OF THE CHILD: Under each heading, please tick the ONE box that you think the child would tick to describe his/her own health TODAY if he/she were able to do so.

**Mobility** (*walking about*)

- He/she has no problems walking about
- He/she has some problems walking about
- He/she has a lot of problems walking about

**Looking after myself**

- He/she has no problems washing or dressing him/herself
- He/she has some problems washing or dressing him/herself
- He/she has a lot of problems washing or dressing him/herself

**Doing usual activities** (*for example, going to school, hobbies, sports, playing, doing things with family or friends*)

- He/she has no problems doing his/her usual activities
- He/she has some problems doing his/her usual activities
- He/she has a lot of problems doing his/her usual activities

**Having pain or discomfort**

[figure not shown]
- He/she has no pain or discomfort
- He/she has some pain or discomfort
- He/she has a lot of pain or discomfort

**Feeling worried, sad or unhappy**

- He/she is not worried, sad or unhappy
- He/she is a bit worried, sad or unhappy
- He/she is very worried, sad or unhappy

**How good is your health TODAY**

- We would like to know how good or bad your health is TODAY.
- This line is numbered from 0 to 100.
- 100 means the best health you can imagine.  
0 means the worst health you can imagine.
- Please mark an X on the line to show how good or bad your health is TODAY.

US (English) © 2012 EuroQol Group. EQ-5D™ is a trade mark of the EuroQol Group

## 18.1.5. HFS Parent Questionnaire

Study ID:

Subject ID:

Today's Date: \_\_\_\_\_ Study ID # \_\_\_\_\_

### University of Virginia Parent Low Blood Sugar Survey

This survey is intended to find out more about how low blood sugar makes people feel and behave. Please answer the following questions as frankly as possible.

I. Below is a list of things parents of children with diabetes sometimes DO IN ORDER TO AVOID LOW BLOOD SUGAR and related problems in their children. Read each item carefully. Circle one of the numbers that best describes YOU.

0 = NEVER    1 = RARELY    2 = SOMETIMES    3 = OFTEN    4 = ALMOST ALWAYS

- |     |  |   |   |   |   |   |
|-----|--|---|---|---|---|---|
| 1.  | Have my child eat large snacks at bedtime.   | 0 | 1 | 2 | 3 | 4 |
| 2.  | Avoid having my child being alone when his/her sugar is likely to be low.                      | 0 | 1 | 2 | 3 | 4 |
| 3.  | Allow my child's blood sugar to be a little high to be on the safe side.                       | 0 | 1 | 2 | 3 | 4 |
| 4.  | Keep my child's sugar higher when he/she will be alone for awhile.                             | 0 | 1 | 2 | 3 | 4 |
| 5.  | Have my child eat something as soon as he/she feels the first sign of low blood sugar.         | 0 | 1 | 2 | 3 | 4 |
| 6.  | Reduce my child's insulin when I think his/her sugar is too low.                               | 0 | 1 | 2 | 3 | 4 |
| 7.  | Keep my child's blood sugar higher when he/she plans to be away from me for awhile.            | 0 | 1 | 2 | 3 | 4 |
| 8.  | Have my child carry fast-acting sugar.   | 0 | 1 | 2 | 3 | 4 |
| 9.  | Have my child avoid a lot of exercise when I think his/her sugar is low.                       | 0 | 1 | 2 | 3 | 4 |
| 10. | Check my child's sugar often when he/she plans to go on an outing.                             | 0 | 1 | 2 | 3 | 4 |
| 11. | Get up in the middle of the night to check on my child or check my child's blood sugar levels. | 0 | 1 | 2 | 3 | 4 |

II Worry: Below is a list of concerns parents of children with diabetes sometimes have. Read each item carefully. Circle one of the numbers that best describes HOW OFTEN YOU WORRY ABOUT EACH ITEM.

0 = NEVER    1 = RARELY    2 = SOMETIMES    3 = OFTEN    4 = ALMOST ALWAYS

12.	Child not recognizing/realizing that he/she is having a low.	0	1	2	3	4
13.	Child not having food, fruit, or juice with him/her.	0	1	2	3	4
14.	Child feeling dizzy or passing out in public.	0	1	2	3	4
15.	Child having a low while asleep.	0	1	2	3	4
16.	Child embarrassing self or friends/family in a social situation.	0	1	2	3	4
17.	Child having a low while alone.	0	1	2	3	4
18.	Child appearing to be "stupid" or clumsy.	0	1	2	3	4
19.	Child losing control of behavior due to low blood sugar.	0	1	2	3	4
20.	No one being around to help my child during a low.	0	1	2	3	4
21.	Child making a mistake or having an accident at school.	0	1	2	3	4
22.	Child getting a bad evaluation at school because of something that happens when his/her sugar is low.	0	1	2	3	4
23.	Child having seizures or convulsions.	0	1	2	3	4
24.	Child developing long term complications from frequent low blood sugar.	0	1	2	3	4
25.	Child feeling light-headed or faint.	0	1	2	3	4
26.	Child having a low.	0	1	2	3	4

